			
changed to reaching the age of 10 years. The following text was modified as follows (bold for additions): The exit date/end of follow-up will be defined as the end of the study period (31 December 2018 for Denmark and 31 December 2019 for Sweden and Norway), death, emigration (where available), reaching the age of 12 years for Denmark and Sweden and the age of 10 years for Norway or date of first diagnosis of the outcome at study, whichever is the soonest.
	
A revised study period starting in 2010 was used instead of starting in 2006 to ensure a 24-month lookback period for the study variables. The follow-up period for the offspring in Norway is up to maximum 10 years of age
	
56	July 2023	9.3.2.2	
In Norway, the exit date/end of follow-up regarding reaching the age of 12 years was changed to reaching the age of 10 years. The following text was modified as follows (bold for additions): The exit date/end of follow-up will be defined as the end of the study period (31 December 2018 for Denmark and 31 December 2019 for Sweden and Norway), death, emigration (where available), reaching the age of 12 years for Denmark and the age of 10 years for Norway or date of first diagnosis of the outcome at study, which-ever is the soonest.
	
Unavailability of Norwegian Patient Registry data before 2008. A revised study period starting in 2010 was used instead of starting in 2006 to ensure a 24-month lookback period for the study variables. The end of follow-up period for the offspring in Norway is, among the others listed that have not changed, reaching the age of 10 years
	Major

Number	Date	Section	Description of change made	Justification	Minor or Major Change
57	July 2023	9.3.2.3	
In Norway, the age of the offspring considered probable or possible case was changed to 10 years rather than of 12 years as in Denmark and Sweden. The following text was modified as follows (bold for additions):
 
 
• Probable case: The offspring aged <math>\leq 12</math> years for Denmark and Sweden and aged <math>\leq 10</math> years for Norway will be considered a probable case if they satisfy the criteria that multiple diagnoses for NDD including ASD are recorded during follow-up, regardless of whether the same code is recorded multiple times or different codes are recorded.
 
• Possible case: The offspring aged <math>\leq 12</math> years for Denmark and Sweden and aged <math>\leq 10</math> years for Norway will be considered a possible case if they satisfy the criteria that only one diagnosis record for NDD including ASD is recorded during follow-up.
 
	
Unavailability of Norwegian Patient Registry data before 2008. A revised study period starting in 2010 was used instead of starting in 2006 to ensure a 24-month lookback period for the study variables. The follow-up period for the offspring in Norway is <math>\leq 10</math> years
	Major
58	July 2023	9.3.3	
The abbreviations reported in the legends for Table 2, Table 3, and Table 4 were updated.
	Editorial change	Minor

Number	Date	Section	Description of change made	Justification	Minor or Major Change
59	July 2023	9.4	Data from the Norwegian Patient Registry was available for record linkage since 2008. The following text was added to Table 5 (bold for additions): Data available for record linkage since 2008.	The updated text reflects the data availability for record linkage in Norway	Major
60	July 2023	9.4 – 9.5 – 9.7.1	
 
The position of the titles for Table 5, Table 6, and Table 7 was moved from below the bodies of the tables to above them.
 
The abbreviations reported in the legends for Table 5 and Table 7 were updated.
 
	Editorial change	Minor
61	July 2023	9.7.2.2	
The entire period for the cumulative incidence proportions in Norway was changed from 0-12 years to 0-10 years. The following text was modified as follows (bold for additions):
 
 
In addition, cumulative incidence proportions for the entire period, 0-12 years for Denmark and Sweden and 0-10 years for Norway, will also be presented; this will be calculated as the total number of offspring experiencing the outcome (NDD and CM, separately) during the entire follow-up (i.e., the sum of the number of events for the years 0
 
	Unavailability of Norwegian Patient Registry data before 2008. A revised study period starting in 2010 was used instead of starting in 2006 to ensure a 24-month lookback period for the study variables. The entire follow-up period for the offspring in Norway is 0-10 years	Major

Number	Date	Section	Description of change made	Justification	Minor or Major Change
			
to 12 for Denmark and Sweden, and 0 to 10 for Norway) divided by the initial number of offspring included at the start of follow-up (i.e., population used in the analysis).
 
 
Furthermore considering index date in the CM cohort will start before or on date of birth and that patients will be followed up until 12 years of age at maximum (10 years of age for Norway), there will be patients with a follow-up longer than 12 years (10 years for Norway), and therefore cumulative incidence proportion for the entire follow-up will include a longer period than 12 years for Denmark and Sweden (but shorter than 13 years).
 
For Norway, the cumulative incidence proportion for the entire follow-up will include a longer period than 10 years, but shorter than 11 years.
 
		
62	July 2023	Annex 3	All tables were formatted, and the legends were included, which report the abbreviations used within the tables.	Editorial change	Minor

Number	Date	Section	Description of change made	Justification	Minor or Major Change
63	July 2023	Annex 4	Table 62 was updated to remove PharmaSwiss, Biomo and Biogaran as they exited the Consortium.	Update of MAH list	Minor
64	August 2023	Abstract: Milestones	Milestones were updated to include additional deliverables, in addition to the original final report of study results, for version 1.1. This version represents the second submission.	Update of deliverables and submission date	Minor
65	August 2023	Milestones	Table 1 was updated to include additional deliverables, in addition to the original final report of study results, for version 1.1. This version represents the second submission.	Update of deliverables and submission date	Minor
66	August 2023	Rationale, Research question and objectives	The following text was modified as follows (strikethrough for deletions): Paternal exposure to valproate will be compared to paternal exposure to lamotrigine or levetiracetam. <del>which are considered a safer treatment (10-13). In women these drugs are generally associated with lower risk of teratogenicity for their offspring but it is unknown whether there effect is the same in men.</del>	Update as per PRAC request	Minor
67	September 2023	PASS Information	MAH participating in Consortium.	Update of MAH list	Minor

## 6. MILESTONES

A progress report is planned 12 months after PRAC endorsement of protocol (Q1 2021) with an interim 6 months after (predicted to be for Sweden and Norway). Due to the long and unknown timeline for data approval, especially in Denmark, the final study report is planned for 23 January 2023. This is because the ethics and data request process in the countries of interest has been known to take anywhere from 6 to 20 months in some cases. Obtaining the data is a pivotal part of producing the interim and final reports. For this reason we propose a progress report, one interim report and one final report (Table 1).

**Table 1: Key milestones**

Milestone	Planned date
Registration in the EU PAS register	Q1 2020 (after endorsement of protocol and before data extraction)
Start of data extraction	Q4 2020
End of data extraction	Q1 2021
Progress report	Q1 2021 (12 months after PRAC endorsement)
Interim report	Q3 2021 (Country-specific)
Final report of study results	23 January 2023, in accordance with PRAC
Final report of study results v1.1, second submission	27 March 2023
Addendum to the final report of study results v1.1 (report on sensitivity analysis 2 and exploratory analysis 8)	27 March 2023
Annex to the final report of study results v1.1 (compilation of sensitivity analysis tables)	27 March 2023
Request for Amendment received from PRAC	05 May-13 June 2023
Partial Responses to List of PRAC Questions	10 July 2023
Submission of the deliverables related to results of the Norwegian re-run analyses	Due 23 October 2023
Submission of updated protocol v7	Due 23 October 2023

EU: European Union; PAS: Post-Authorisation Study; PRAC: Pharmacovigilance Risk Assessment Committee

The conditions to market authorisation require that the study protocol is submitted in accordance with article 107n (1) of directive 2001/83/ec within 6 months after commission decision (received on 31 May). A progress report shall be submitted to the PRAC within 12 months after PRAC endorsement. An interim report will be submitted to the PRAC 6-months after, and the final report in the 23 January 2023, as in accordance with PRAC.

## 7. RATIONALE AND BACKGROUND

### 7.1 Background

Valproate-containing medicines are approved nationally in the EU to treat epilepsy and bipolar disorder. It is also approved in some countries for prevention of migraine, but not supported by all MAHs. In recent years, due to an increased risk of neurodevelopmental disorders (NDD) including autism spectrum disorders (ASD), and congenital malformations (CM) in offspring after valproate exposure in utero, the use of valproate has been restricted to cases in which no other effective or tolerated treatment is available in women of childbearing potential or in pregnant women suffering from epilepsy; it has been contraindicated in pregnant women suffering from bipolar disorder (2).

While the effects of maternal exposure of drugs during pregnancy on offspring outcomes are widely studied, the role of paternal exposure to drugs prior to conception on offspring's health has not yet been clearly demonstrated. Evidence from paternal exposure to radiation, antimetabolic drugs or environmental toxins suggest that (epi-)genetic modifications may be transmitted through the father to the next generation. Engeland et al. studied the possible association between drugs dispensed to the father in the 3 months prior to conception and adverse pregnancy outcomes (3), with no strong conclusion.

Previous literature found that paternal exposure to valproate in mice might lead to behavioral alterations in offspring (4). It is still unclear if these results may be translated to the human population.

The spermatogenic cycle in humans lasts about 74 days (2.5 months) (5), which may be a vulnerable time for acute exposures such as drug intake. Large population-based studies addressing the associations between increased risk of adverse outcomes in the offspring following paternal exposure to drugs prior to conception are rare, as few databases offer the possibility of paternal-offspring linkage, and the effect of the paternal exposure may be very small. Thus far, only one study based on Danish national registers has reported an increased risk of ASD following paternal use of selective serotonin reuptake inhibitors (SSRIs) before conception (6), and concluded that the increased risk of ASD in the offspring associated with paternal SSRI use before conception may be attributable to paternal underlying psychiatric indications related to SSRI use or other unmeasured confounding factors. Other studies which evaluated the paternal exposure to Disease-Modifying Antirheumatic Drugs in Norwegian registries (7), or a large number of different prescription drugs in Norwegian registries including antiepileptic drugs (AEDs) (3,8), did not find an increased risk for adverse outcomes in offspring. Specifically, the risk of paternal exposure to valproate has thus far not been found to significantly affect offspring's outcomes (3,9).

### 7.2 Rationale

There is currently scarce real-world evidence of an increased risk of NDD including ASD, or CM in offspring following paternal exposure to AEDs. Therefore, following the Pharmacovigilance Risk Assessment Committee (PRAC) recommendation dated 08 February 2018, this post-authorisation safety study (PASS) is being conducted to evaluate the association between paternal exposure to valproate and risk of NDD, including ASD, as well as CM in offspring.

## 8. RESEARCH QUESTION AND OBJECTIVES

The aim of this retrospective cohort study is to examine the association between paternal exposure to valproate at conception and the risk of NDD, including ASD, as well as CM in offspring. Paternal exposure to valproate will be compared to paternal exposure to lamotrigine or levetiracetam.

### Primary objective

1. Investigate the risk of NDD, including ASD, in offspring paternally exposed to valproate (monotherapy), compared to lamotrigine or levetiracetam (composite monotherapy) treatment at the time of conception.

### Secondary objectives

2. Investigate the risk of CM in live and non-live offspring paternally exposed to valproate (monotherapy), compared to lamotrigine or levetiracetam (composite monotherapy) treatment at the time of conception, in Norway and Denmark.
3. Describe AED exposure (posology and duration) data and health characteristics of male patients prescribed AEDs (including valproate and lamotrigine/levetiracetam) in treatment of epilepsy and other indications at the time of conception of their offspring, both for NDD and CM cohort.
4. Identify potentially important risk factors for outcomes of interest, in offspring paternally exposed to valproate (monotherapy) or lamotrigine or levetiracetam (composite monotherapy) at the time of conception, by examining AED exposure and health characteristics of the offspring and their mothers.

### Exploratory objectives

[figure not shown]
5. To describe the putative risk factors and frequency of NDD, including ASD, as well as CM in offspring paternally exposed to valproate (in combination with other AEDs) and to other AEDs (in combination with other AEDs, excluding valproate) at the time of conception.
6. To describe the risk factors and frequency of NDD, including ASD, as well as CM in paternally and maternally matched exposure-discordant (valproate vs lamotrigine/levetiracetam monotherapy) siblings at conception.
7. Investigate the risk of CM in live offspring paternally exposed to valproate (monotherapy), compared to lamotrigine or levetiracetam (composite monotherapy) treatment at the time of conception in Sweden.
8. To describe the frequency of CM by target body system organ class in live and non-live offspring paternally exposed to valproate (monotherapy), and to lamotrigine or levetiracetam (composite monotherapy) treatment at the time of conception.

## 9. RESEARCH METHODS

### 9.1 Study Design

[figure not shown]
The study will be carried out using a retrospective non-interventional longitudinal population-based cohort design conducted using secondary data derived from multiple registry databases recording longitudinal medical data in Sweden, Norway, and Denmark. The aim is to study the risk of NDD including ASD, as well as CM in offspring following paternal exposure to valproate.

For the evaluation of NDD, including ASD, the population for analysis will be comprised of live births for whom medical record linkage to mother and father is available within such registries. For the evaluation of CM, the population for analysis will be comprised of live births, stillbirths and spontaneous abortions during gestation (2nd and 3rd trimester) for whom medical record linkage to mother and father is available within such registries, for Norway and Denmark. For Sweden the corresponding population for analysis will be comprised of live births only. The primary outcome of interest is NDD, including ASD in offspring up to 12 years of age based on ICD-10 diagnostic codes, as recorded in the National Patient Registries. The secondary outcome of interest is a composite of CM diagnosed in offspring up to 12 years of age, stillbirths and spontaneous abortions-based on ICD-10 diagnostic codes, as recorded in the National Patient Registries and Medical Birth Registries. The primary exposure of interest is paternal use of valproate during the spermatogenic risk window prior to conception of the offspring (defined by the first day of the last menstrual period date plus two weeks [LMP2] of the mother within the linked family unit). Exposure information will be derived from prescription data, as recorded in the National Prescription Registries for each country (from 2005 in Sweden, 2008 in Norway and 1995 in Denmark) to 31 December 2018 for Denmark and 31 December 2019 for Sweden and Norway. Country-specific cohorts of eligible linked family units will be identified. These cohorts (in terms of aggregated results) will be combined into an all-Nordic cohort (Sweden, Norway, Denmark for the primary outcome and Norway, Denmark for the secondary outcome) where feasible to further increase validity and statistical power. An overview of the study design for the primary and secondary outcomes are provided in Figure 1 and Figure 2.

**Figure 1: Overview of the study design for evaluating the primary outcome**

 Data about voluntary or medically required abortions, that can have a diagnosis of CM, are not linked to fathers in none of the countries at study.

**Figure 2: Overview of the study design for evaluating the secondary outcome**

## 9.2 Setting

For real-world evidence generation, secondary longitudinal data sources can offer insights into clinical characteristics and outcomes. However, linkage of fathers to offspring is rare in most European countries, as typically only the mother is linked to the offspring within the data. It is also rarely noted in the record of a man, that they became a father. The exception of this are Scandinavian countries, which offer the possibility to link paternal data to offspring using national identification numbers and registers. This study widens the population size and broadens the geographic scope compared to the previous studies on valproate and offspring outcomes (10–13). This study will therefore focus on the three Scandinavian countries: Sweden, Denmark, and Norway.

### 9.2.1 Study time period

The study time period will be based on availability of information from the National Registries; this will start from 01 January 2007 in Sweden, 01 January 2010 in Norway, and 01 January 1997 (01 April 2004 for secondary outcome) in Denmark in order to allow for 24 months average look back period for live births:

- pregnancy duration (9-months on average for live births),
- maternal and paternal preconceptional exposure (3-months),
- minimum look back period for confounders (12-months).

The study time period ends on 31 December 2018 for Denmark and 31 December 2019 for Sweden and Norway. The rationale for this choice is to include all data available from relevant

 In Denmark, for the period 1997-1 April 2004, stillborns born between 22nd and 28th weeks of gestation are not included in the Medical Birth Register but in the National Patient Register. However, since in the National Patient Register the linkage with the father is not available, the study period for the secondary outcome in Denmark is limited to 2004-2017 (or last available date).

linked registers, to capture a sufficient number of outcomes and exposures and linked family units, and to include the most up-to-date data available.

### 9.2.2 Participants

Since this is a non-interventional observational study, minimal inclusion and exclusion criteria are desirable to minimise potential selection bias and represent real clinical practice. The following selection criteria will be applied for the data extraction:

#### Inclusion criteria for data extraction

- Singleton pregnancies, with known pregnancy-length of at least 12 weeks within the study time period;
- Pregnancies linked to both mother and father within the study time period;
- Father with a continuous enrolment in the database for  $\geq 12$  months prior to linked mother LMP2 date;
- Father with at least one AED in the data available.

For Sweden the inclusion criteria are slightly different, as only live births can be included:

- Singleton pregnancies resulting in live births
- Pregnancies linked to both mother and father within the study time period;
- Father with a continuous enrolment in the database for  $\geq 12$ -months prior to linked mother LMP2 date;
- Father with at least one exposure to AED during 192 days prior to 28 days after LMP2 date

#### Exclusion criterion for data extraction

- Adopted children
- Pregnancy associated with in vitro fertilisation (IVF)
- Pregnancies with missing gestational age and/or missing maternal LMP2 (for these pregnancies it will not be possible to identify the exposure window for the study)

To address the research questions related to the primary outcome (NDD including ASD) and secondary outcome (CM) two separate cohorts will be created, and additional selection criteria, nested within the criteria for data extraction, will be applied (see Section 9.2.2.1). These cohorts will from now on be referred as the primary and secondary outcome cohort.

---

 Twins were excluded because they share the same paternal exposure and it is not known how medication can be absorbed, distributed and metabolised by each of them. Moreover preterm birth and low birth weight (associated with NDD and CM) occur more frequently in twin and triplet pregnancies than in singleton pregnancies.

 Pregnancy terminations (e.g. spontaneous abortions) before 12 weeks gestation are not recorded in the data sources.

 A patient is considered continuously enrolled in a specific time period if that patient had a contact with healthcare services (such as drug prescription or hospitalisation) prior to that period and if emigration or death were not notified after this contact.

### **9.2.2.1 Neurodevelopmental disorders, including ASD**

The following inclusion and exclusion criteria will be applied, after data extraction, to create a family linked cohort with the objective of investigating the risk of NDD, including ASD, in offspring paternally exposed to valproate.

#### Inclusion criteria for the primary outcome cohort

- Singleton born alive within the study time period (i.e. the birth of only one child during a single delivery)
- Mother with a continuous enrolment for  $\geq 12$ -months prior to child birthdate

#### Exclusion criteria for the primary outcome cohort

- Offspring whose parent(s) have a history of CM or NDD (according to available records)

### **9.2.2.2 Congenital malformations**

The following inclusion and exclusion criteria will be applied, after data extraction, to create a family linked cohort with the objective of investigating the risk of CM in offspring paternally exposed to valproate.

#### Inclusion criterion for secondary outcome cohort

- Mother with a continuous enrolment of 12-months prior to index date (12th week of gestation in Norway, 22nd week of gestation in Denmark, and birthdate of live offspring in Sweden)

#### Exclusion criterion for secondary outcome cohort

- Offspring whose parent(s) have a history of CM or NDD (according to available records)

## **9.2.3 Overview of the family linkage**

### **9.2.3.1 Neurodevelopmental disorders, including autism**

[figure not shown]
For the purpose of the evaluation of NDD, including ASD, Figure 3 illustrates the registry linkage of the study participants, the paternal exposure period (3-months prior to LMP2 date, for further details please see footnote 10), follow-up period for the offspring (from birth to maximum 12 years of age for Denmark and Sweden and 10 years of age for Norway), and the look back periods for confounders for each linked family member (mother: 12 months prior to delivery, father: 12 months prior to LMP2 date).

---

 Non-live births are not included because a diagnosis of NDD cannot be made

 A patient is considered continuously enrolled in a specific time period if that patient had a contact with healthcare services (such as drug prescription or hospitalisation) prior to that period and if emigration or death were not notified after this contact.

[figure not shown]
 A patient is considered continuously enrolled in a specific time period if that patient had a contact with healthcare services (such as drug prescription or hospitalisation) prior to that period and if emigration or death were not notified after this contact.

[figure not shown]

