#### Additional inclusion criteria for the primary outcome (NDD including ASD)

- Singleton born alive within the study time period (i.e. the birth of only one child during a single delivery)
- Mother with a continuous enrolment for  $\geq 12$  months prior to child birthdate

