#### Additional inclusion criteria for the secondary outcome (CM)

- Mother with a continuous enrolment of 12 months prior to index date (12th week of gestation in Norway, 22nd in Denmark, offspring birth date in Sweden)

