**Table 2: Potential risk factors for NDD**

Mother	Father	Offspring

 
• Age
 
• Obesity (12 months look back from LMP2) 
 
• Smoking (12 months look back from LMP2 and DP)
 
• Substance abuse (12 months look back from LMP2 and DP)
 
• Alcohol abuse (12 months look back from LMP2 and DP)
 
• Schizophrenia, schizotypal and delusional disorders (ever)
 
• Affective Disorder (ever)
 
• Neurotic Disorder (ever)
 
• Rubella (DP)
 
• CMV (DP)
 
• Diabetes (ever) & Gestational Diabetes (DP)
 
• Any concomitant medications associated with valproate-indicated psychiatric conditions (12 months look back from LMP2 and DP) 
 
• Any concomitant medications associated with neuropsychiatric adverse effects (12 months look back from LMP2 and DP) 
 
	
 
• Substance Abuse (12 months look back from LMP2)
 
• Affective Disorders (excluding bipolar and mania) (ever)
 
• Schizophrenia, schizotypal and delusional disorders (ever)
 
• Neurotic Disorder (ever)
 
• Any concomitant medications associated with valproate-indicated psychiatric conditions (12 months look back from LMP2) 
 
• Any concomitant medications associated with neuropsychiatric adverse effects (12 months look back from LMP2) 
 
	
 
• Sex
 
• Foetal Alcohol syndrome
 
• Fragile X Syndrome
 
• Congenital CMV
 
• Congenital Rubella
 
• Lejeune/ cri du chat syndrome
 
• Tuberous sclerosis
 

 In addition to recognised risk factors, any co-medications received (including other psychoactive treatments received) during the exposure periods described in section 9.3.1, will be investigated and adjusted for in the analysis using a polypharmacy index.

NDD: Neurodevelopmental disorders; LMP2: Last Menstrual Period + 2 weeks; DP: during pregnancy; CMV: Cytomegalovirus

Omitted from this list are

- risk factors that are exclusion criteria for comparative, sensitivity and exploratory objective analyses:
  - mother: history of epilepsy and NDD,
  - father: history of NDD,
  - child: exposure to AEDs and diagnosis of epilepsy after birth
- paternal factors listed in Table 4.

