## **9.4 Data Sources**

The proposed sources of data are expected to provide a rich set of variables. Given the real-world, retrospective nature of the data, the availability of complete information is expected to vary.

All data elements for this study will be collected from information routinely recorded in the national registries of

---

 In order to account for potential dispensations that can have led to an intake during the 3 months look-back period under investigation, all dispensations that are recorded in the 6 months before conception that gave rise to a teratogenic drug intake during the 3 months prior to conception will be considered.

 See footnote 14

- Sweden
- Norway
- Denmark

Databases used in the study are listed in Table 5. Sweden will not be used in the secondary outcome cohort analysis due to lack of paternal linkage to non-live births.

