## Sweden

Individual patient data is collected from both in- and outpatient hospital based specialist care across all of Sweden. The National Patient Register dates back to 1964. From 1987 onward, there is information on all completed inpatient admissions across the country. The collection of outpatient care data began in 2000. The register is updated annually and available from September/October the following year.

All medicines are prescribed electronically in Sweden. The National Prescription Register tracks the full details of all dispensed medications at individual patient-level in Sweden since 01 July 2005. Patients are followed longitudinally through their personal identification number, regardless of which pharmacy they visit. The National Prescription Register is updated monthly and covers all sales of dispensed medication from Swedish pharmacies.

The Medical Birth Register contains information about all pregnancies resulting in delivery in Sweden and is frequently used for quality improvement work and for research. The register contains detailed information about mothers and births. The Swedish Multigeneration Register was established in 1973, and contains information on more than nine million individuals. Data on mothers are available in 97% and on fathers in 95% of index people (those born from 1932 onwards and those alive on 01 January 1961). Individual-level data on breastfeeding is not available in the Swedish registers.

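### Maternal look-back and enrolment are anchored at birth or the CM index date although maternal covariates are measured over 12 months before LMP2, and the stated 24-month look-back is 18 months for Swedish dispensing data

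*Protocol*

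**What the plan says.** **Maternal window and enrolment.** For NDD, section 9.2.3.1 describes the "look back periods for confounders for each linked family member (mother: 12 months prior to delivery, father: 12 months prior to LMP2 date". Section 9.2.3.2 gives the CM mother a minimum of 12 months before the index date. Eligibility uses the same anchors. The NDD cohort (section 9.2.2.1 and the abstract) asks for at least 12 "months prior to child birthdate". The CM cohort (section 9.2.2.2 and the abstract) asks for "Mother with a continuous enrolment of 12 months prior to index date", which is gestational week 12 in Norway, week 22 in Denmark and birth in Sweden. The father's enrolment in section 9.2.2 is counted back from LMP2.

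**Covariate definitions.** Table 2 lists, for the mother, "Substance abuse (12 months look back from LMP2 and DP"), and treats smoking, alcohol abuse and co-medications in the same way. Obesity uses the 12 months before LMP2 without pregnancy. Table 3 does the same for CM, without the co-medications. Annex 3D and the CM part of Annex 3F repeat these windows, as binary yes/no variables. For the teratogen exclusion, footnote 14 draws on "all dispensations that are recorded in the 6 months before conception that gave rise to a teratogenic drug intake".

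**Calendar start.** Section 9.2.1 sets the start dates, including 1 January 2007 for Sweden, "in order to allow for 24 months average look back period for live births". It builds this from 9 months of pregnancy, 3 months of preconception exposure and 12 months for confounders. Section 9.4.1 says the Swedish prescription register "tracks the full details of all dispensed medications at individual patient-level in Sweden since 01 July 2005".

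**The concern.** For a term birth, 12 months before delivery and 12 months before LMP2 start about nine months apart, so a programmer cannot follow sections 9.2.3.1 and 9.2.3.2 and the covariate tables at once. If eligibility follows the first and covariates the second, a mother with the minimum history has a covariate window that is partly unobserved. Because the variables are yes/no, unobserved history becomes a negative. It is not recorded as missing, so the missingness summaries in section 9.7.7 would not show it. These maternal items are risk factors and not Table 4 confounders, but section 9.7.3.2.3 allows outcome-related variables from section 9.3.3 into the propensity score, so they can reach the adjusted analysis.

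The Swedish point is separate. The 24-month figure is the stated reason for the start date, and for one of the registers it is not met.

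**Working it through.** **Inputs.** LMP2 is LMP plus two weeks (section 9.1), so days from LMP2 to gestational week *g* are 7 × (*g* − 2). Term is taken as 40 weeks (an assumption); 37 and 42 weeks give the range. Enrolment is 365 days before the anchor.

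**1. The plan's own figure.** 9 + 3 + 12 = 24 months reproduces. Denmark (dispensing from 1995, start January 1997) and Norway (patient registry linkage from 2008, start January 2010) both give 24 months.

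**2. Minimum maternal record before LMP2** = 365 − 7 × (*g* − 2).

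| Cohort | Anchor | Days from LMP2 to anchor | Assured days before LMP2 | Short of 365 |
|---|---|---|---|---|
| NDD, all countries; CM Sweden | birth, 40 weeks | 266 | 99 (3.3 months) | 266 |
| CM Denmark | week 22 | 140 | 225 (7.4 months) | 140 |
| CM Norway | week 12 | 70 | 295 (9.7 months) | 70 |

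For the birth anchor, 37 weeks gives 365 − 245 = 120 days and 42 weeks gives 365 − 280 = 85 days.

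**3. Against footnote 14** (6 months, about 182 days). Denmark (225) and Norway (295) exceed it. Swedish CM at term falls short by 182 − 99 = 83 days. The 99 days still cover the 3-month intake window of about 91 days, so what is at risk is carry-over from earlier dispensings.

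**4. Swedish calendar coverage.**

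- 1 July 2005 to 1 January 2007 is 18 months (549 days), not 24.
- A term birth on 1 January 2007 has LMP2 on 10 April 2006 (266 days earlier). Its 12-month window opens on 10 April 2005, 82 days before the register starts.
- Cross-check: the window needs 266 + 365 = 631 days before birth, and 631 − 549 = 82.
- First term birth with a complete window: 1 July 2005 + 631 days = 24 March 2007.
- Affected share: 82 of the 4,748 days from 1 January 2007 to 31 December 2019 = 1.7%.
- The paternal exposure look-back (192 days before LMP2 in the Swedish extraction criterion) reaches 30 September 2005 for the earliest birth, which the register covers. A 6-month look-back reaches 9 October 2005, also covered.

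**The case against.** Several things limit the consequence, and they stand.

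- **Enrolment is a floor.** The registers are national and a resident mother will normally have the full window. The footnotes defining enrolment also require a healthcare contact before the 12-month period, so an eligible mother's first record is earlier than the figures above. They are lower bounds.
- **Few mothers would be miscoded.** Every listed maternal item with a 12-month window except obesity also counts pregnancy. Annex 3 takes smoking, and obesity for CM, from the Medical Birth Registry. A wrong negative needs a late-starting record and a code that falls only in the unobserved months and does not recur in pregnancy.
- **The teratogen shortfall is narrow.** It is confined to Swedish CM, which is exploratory objective 7 and is presented separately.
- **Swedish diagnoses are not affected.** Inpatient data are national from 1987 and outpatient data begin in 2000 (section 9.4.1).
- **A stricter rule has a price.** Section 9.2.2 prefers minimal criteria in order to limit selection bias.

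A reader might also infer that Norway's start was moved to 2010 for the same reason that Sweden's should be. The amendment log gives the reason as Norwegian patient registry data being unavailable before 2008. Norwegian dispensing goes back to 2004 (Table 5), so the two cases concern different registers.

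None of this reconciles the two maternal windows. The word average in section 9.2.1 allows for varying pregnancy length but does not explain a six-month gap in Sweden.

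**Conclusion.** The point holds as an internal contradiction and a wrong stated figure, with a small expected effect.

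- **Maternal window.** The stated look-back and enrolment anchor disagree with the covariate definitions. The rule assures 99, 225 or 295 days before conception where the covariates need 365. The number of mothers with only the minimum history is not in the document. A range of 1–5% is an assumption, and no bias in the hazard or odds ratio can be derived from it.
- **Sweden.** Dispensing look-back at the study start is 18 months. The data loss is in the 12-month co-medication covariates of both parents, for term births over 82 days, 1.7% of Swedish study time. Table 3 has no co-medication items, so this concerns the NDD cohort.

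Stronger readings are not supported. One might take the 99 days as all the maternal history available; it is a minimum. One might conclude that the primary outcome is handled differently by country; the NDD enrolment rule is identical in all three, and only the CM anchors differ, as section 9.9.1 already acknowledges for the index dates. One might think the Swedish gap truncates paternal exposure; it does not. One might count all births before 1 July 2007 as deficient (6 of 156 months, 3.8%); that measures failure to meet the 24-month label, whereas the covariate window for a term birth needs about 20.7 months.

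**What to change.** 1. In sections 9.2.3.1 and 9.2.3.2, state the maternal look-back as 12 months before LMP2 through the index date, matching Tables 2 and 3 and Annex 3.
2. In sections 9.2.2.1 and 9.2.2.2 and the abstract, require maternal enrolment for at least 12 months before LMP2 through the index date, as section 9.2.2 does for fathers before LMP2. This means re-running the cohort filter and loses mothers with short records. If that selection is unwelcome, keep them, flag incomplete look-back, and repeat the adjusted analyses without them as a sensitivity run.
3. In section 9.2.1, state that Swedish dispensing look-back is 18 months at the study start, and exclude Swedish births whose 12-month pre-LMP2 window begins before 1 July 2005. At term this removes births before about 24 March 2007. Moving the whole Swedish start to 1 July 2007 is not needed and would discard about three months of births with complete windows.
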